2. Mod-step: the concentration-response curve will be characterized, and the minimum effective concentration and optimal concentration will be estimated. All significant models indicated by the previous step will be fitted, and minimum effective concentration and optimal concentration will be estimated based on the fitted models.
3. Finally, weighted estimates for minimum effective concentration and optimal concentration will be calculated using weighing in Buckland et al. ([Buckland 1997](#)).

The above analysis will be performed on the modified intent-to-treat set and PP set; the modified intent-to-treat set will be used as the primary analysis set.

The change from baseline and percent change from baseline in Pruritus NRS will be analyzed using a mixed effects model with baseline pruritus NRS as covariate, treatment, visit, treatment by visit as fixed effects, participant as random effects. With fitted model, the least square means and their 95% confidence intervals, the least mean differences between each active treatment and placebo and their 95% confidence intervals will be calculated for Week 1, 2, 3, and 4.

The change from baseline and percent change from baseline in Pruritus NRS will also be summarized by treatment and visit using descriptive statistics.

The above analysis will be performed on the modified intent-to-treat and PP sets.

Pruritus response, which is defined as improvement (reduction) of 7-day average of daily hand peak pruritus NRS ≥ 4 from Baseline, will be analyzed using the Cochran Mantel Hansel test, controlling for NRS at baseline, at Week 1, 2, 3, and 4.

Pruritus response will also be summarized descriptively by treatment and visit.

Pruritus response will be analyzed on both the modified intent-to-treat and PP sets.

All other continuous variables will be analyzed in a similar manner as the percent change from baseline in Pruritus NRS; all other binary variables will be analyzed in a similar manner as the Pruritus response.

All efficacy variables will be listed for each participant by visit.

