## 5 GENERAL CONSIDERATIONS

### 5.1 Sample Size

For the primary endpoint analysis of the percent change of 7-day average daily peak pruritus NRS from Baseline to Week 4, N = 24 / group will give us 80% power to detect a standardized effect of 0.72 with 2-sided significance level of 0.1 (28.8% improvement over placebo in % change from baseline in pruritus, assuming standard deviation [SD] = 40%).

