## **6 STATISTICAL CONSIDERATIONS**

### **6.1 General Statistical Considerations**

The significance level for this trial is set to be 2-sided 0.05 unless otherwise specified. For PK data, geometric mean and percent of coefficient of variance (%CV) will be presented.

All decimal places will be kept to 3 places or less.

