## **13.2 Key Secondary Endpoints**

The following continuous secondary efficacy endpoints, as defined in [section 5.7](#), will be analyzed using MMRM model with visit, treatment and visit by treatment interaction as fixed effects, baseline NRS as covariate, participant as random effects will be fitted first, the ls means and their variance-covariance matrix at Week 4 will be estimated using the fitted model. Percent change of 7-day average daily peak pruritus NRS from Baseline to Week 1, 2, and 3.

- Change of 7-day average daily peak pruritus NRS from Baseline to Week 1, 2, 3 and 4.
- Change and percent change from baseline in daily peak pruritus NRS from Days 1 to 7.
- Change from baseline in 5-D Pruritus Scale at Week 2 and 4.
- Change and percent change from baseline in the EASI score at Week 2 and 4.
- Change from baseline in total BSA at Week 2 and 4.
- Change from baseline in the Dermatology Life Quality Index (DLQI) at Week 2 and 4.
- Change from baseline in The Patient Oriented Eczema Measure (POEM) at Week 2 and 4.

The endpoints will be summarized by visit presenting LS Mean, 95% CI and associated p-value from the above MMRM model, using mITT analysis set and PP set.

The following categorical secondary efficacy endpoints will be analyzed based on Fisher's exact test. In addition, odds ratio (OR) and 95% Wald confidence intervals will also be presented when applicable:

- Pruritus response is defined as the 7-day average of daily peak pruritus NRS reduction  $\geq 4$  points from Baseline at Week 1, 2, 3, and 4.

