## **13.3 Exploratory Endpoints**

The following categorical exploratory endpoints will be summarized using mITT analysis set. P-values and 95% confidence intervals (CI) will be presented based on Fisher's exact test. In addition, odds ratio (OR) and 95% Wald confidence intervals will also be presented when applicable:

- At least a 50% reduction from baseline in EASI-50 at Week 2 and 4.
- At least a 75% reduction from baseline in EASI-75 at Week 2 and 4.
- At least a 2-grade reduction from Baseline to clear (0) or almost clear (1) in vIGA at

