## **15 CHANGES FROM PROTOCOL**

- Added “analyses of adverse events will include all events reported from the time of informed consent to 28 days after the last dose of study drug” to AE definition.
- Added “receive at least 1 dose of treatment” to the definitions of all the analysis sets.
- Updated the definition of the Per protocol population.
- Updated the analysis of categorical efficacy endpoints to use Fisher exact test instead of the CMH test.

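### The SAP swaps the protocol's baseline-controlled CMH test for Fisher's exact test on the responder endpoints without giving a reason; under assumed response rates this costs roughly 10 points of power, and the planned Wald interval can contradict the p-value.

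*SAP*

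**What the plan says.** Protocol 9.3.1 says that pruritus response (a drop of at least 4 points in the 7-day average) "will be analyzed using the Cochran Mantel Hansel test, controlling for NRS at baseline, at Week 1, 2, 3, and 4", and that "all other binary variables will be analyzed in a similar manner as the Pruritus response". It names no baseline strata and does not say whether a continuity correction applies.

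SAP 13.2 replaces this: "The following categorical secondary efficacy endpoints will be analyzed based on Fisher's exact test". No covariate or stratum is mentioned. Beside the p-value, "odds ratio (OR) and 95% Wald confidence intervals will also be presented when applicable"; no other interval is planned for pruritus response. SAP 13.3 treats EASI-50, EASI-75 and the vIGA responder endpoint alike, but there "P-values and 95% confidence intervals (CI) will be presented based on Fisher's exact test", with the Wald odds-ratio interval in addition.

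SAP 15 lists the switch: "Updated the analysis of categorical efficacy endpoints to use Fisher exact test instead of the CMH test". No reason follows. The default in SAP 6.1 applies to these tests: "The significance level for this trial is set to be 2-sided 0.05 unless otherwise specified".

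**The concern.** Fisher's test conditions on both margins. In arms of 24 to 30 its attainable p-values are coarse, so a nominal 5% test rejects much less often than 5% of the time, and power falls with it. The protocol's test need not pay this price.

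The switch also drops baseline NRS. Entry requires a score of at least 7, so a 4-point fall is 57% of a baseline of 7 but 40% of a baseline of 10. The SAP keeps baseline NRS as a covariate in the MMRMs for the same score and omits it only for the responder version.

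Finally, a Wald interval for the odds ratio does not invert Fisher's test. The table for pruritus response could show an interval excluding 1 beside a non-significant p-value, and the SAP does not say which to believe.

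**Working it through.** **The plan's own figure.** The only power statement concerns the continuous primary endpoint: "N = 24 / group will give us 80% power to detect a standardized effect of 0.72 with 2-sided significance level of 0.1". It reproduces: 28.8/40 = 0.72; 2 × (1.645 + 0.842)² / 0.72² = 23.9, so 24 per group; power = Φ(0.72 × √12 − 1.645) = Φ(0.849) = 80.2%. No figure is given for any responder endpoint.

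**Inputs.** From the documents: two-sided 0.05, 24 (sample-size statement) or about 30 (planned) per arm, baseline NRS of at least 7. Assumed: each concentration is compared separately with vehicle; the response rates; a baseline mix for scores 7/8/9/10 of 35/35/20/10%; and a log-odds slope of 0, 0.5 or 1.0 per baseline point.

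The plan's planning values give a rough anchor. Take percent improvement as Normal with SD 40 and mean 10 (vehicle) or 40 (active). From a baseline of 8, response means at least 50% improvement: 1 − Φ(1.00) = 15.9% against 1 − Φ(0.25) = 40.1%. In the active arm the rate runs from 1 − Φ((57.1 − 40)/40) = 33.4% at baseline 7 to 50% at baseline 10. The implied slope is −ln(0.334/0.666)/3 = 0.23 per point, between the 0 and 0.5 settings.

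**Formulas.** For stratum k, with a responders on active out of n_T, n_C on vehicle, m responders among N in total:

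CMH = [Σ(a − n_T·m/N)]² / Σ[n_T·n_C·m·(N − m) / (N²(N − 1))], compared with 3.84. The continuity-corrected form subtracts 0.5 from the absolute sum before squaring. The Wald interval is exp(ln OR ± 1.96 × √(sum of the reciprocals of the four cells)).

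**True level.** By exact enumeration, at a common response rate of 15% and 20%, Fisher's level is 2.4% and 2.6% at n = 24, and 1.7% and 2.2% at n = 30 (1.6% in one simulated set). The unstratified, uncorrected Mantel-Haenszel (MH) test has 4.9-5.4%. A simulated uncorrected CMH with strata 7-8 and 9-10 stays at or below 5.2% for null rates of 3% to 20%.

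**Power** (slope 0.5, 20,000 simulated trials per row, two strata):

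| n per arm | Rates | Fisher | CMH, uncorrected | Difference | CMH, corrected |
|---|---|---|---|---|---|
| 30 | 15% vs 40% | 48.7% | 60.2% | 11.5 | 47.0% |
| 30 | 20% vs 50% | 59.5% | 70.5% | 11.0 | 59.5% |
| 24 | 15% vs 40% | 39.7% | 50.6% | 10.9 | 36.2% |

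The simulation error of one entry is at most √(0.25/20,000) = 0.35 points. With slope 0 the difference is still 9 to 10 points; with slope 1.0 it is 14 to 16. In exact enumeration against the unstratified MH test at n = 30, it is 10.6 points at 15.9% vs 40.1%, and ranges from 3.5 (10% vs 50%) to 21.2 (5% vs 20%).

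**Source of the loss.** At n = 30 and 15% vs 40%, the unstratified uncorrected MH test already reaches 59.6%. Of the 11.5 points, 59.6 − 48.7 = 10.9 come from exact against uncorrected asymptotic testing and 60.2 − 59.6 = 0.6 from stratifying. Over three scenarios at slope 0.5, stratifying adds 0.6 to 1.3 points. At slope 0 it loses up to 1 point; at slope 1.0 it adds about 5.

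**Interval against p-value.** Take 10/30 against 3/30. OR = (10 × 27)/(20 × 3) = 4.5. The standard error is √(1/10 + 1/20 + 1/3 + 1/27) = 0.721, so the Wald interval is exp(1.504 ± 1.414) = 1.09 to 18.5. Fisher gives p = 0.057. On the same table the uncorrected MH statistic is 3.5²/2.589 = 4.73 (p = 0.030), where 2.589 = 30 × 30 × 13 × 47/(60² × 59). The corrected one is 3.0²/2.589 = 3.48 (p = 0.062). A second case: 11/30 against 4/30 gives p = 0.072 with a Wald interval of 1.04 to 13.6. A Wald interval excluding 1 with Fisher p>0.05 occurs in about 7-10% of comparisons at 15-20% vs 40-50%, and in about 1-12% across the grid.

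**The case against.** The best defence is that Fisher's test is valid at any sample size, applies one rule to sparse cells (early weeks, EASI-75, vIGA clear or almost clear), and is openly declared. No decision in either document rests on a responder p-value: treatment effect, minimum effective concentration and optimal concentration all come from MCPMod. All of this stands and limits the importance of the point. What it does not show is a gain in validity, because the uncorrected two-stratum CMH also held its level in simulation.

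A sharper objection also stands. The protocol never specified an uncorrected test or the strata, and a continuity-corrected CMH does no better than Fisher (last column of the table). A reader might infer that the SAP gave up power the protocol had already secured. The documents do not support that, since the protocol wording allows either form. The gain comes from a fully specified, uncorrected CMH.

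A reader might also infer that the lost baseline adjustment causes the power loss. The decomposition above shows otherwise unless baseline is strongly prognostic, and the documents contain no data on that.

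**Conclusion.** The point holds as an inexpensive improvement to secondary and exploratory analyses. The SAP makes a disclosed but unexplained change to a test whose true level is about half the nominal 5% or less. The cost is roughly 10 points of power against an uncorrected CMH: about 9 to 11 points at 15-20% vs 40-50% with slopes of 0 to 0.5, with single scenarios slightly outside that band. The size rests on assumed response rates, baseline mix and slope, and on omitting the continuity correction; across the wider rate grid it is 3.5 to 21 points.

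The mismatch between p-value and interval is possible in a minority of comparisons, not the rule. It matters most for pruritus response, where the Wald interval stands alone; for the exploratory endpoints a Fisher-based interval is planned as well.

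Three stronger readings fail. The change is not hidden, because SAP 15 lists it. Type I error is not inflated, because Fisher errs on the safe side. The primary MCPMod analysis and its sample size are untouched.

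**What to change.** In SAP 13.2, and for the binary endpoints in 13.3:

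- Return to the CMH test for each concentration against vehicle. Define the baseline-NRS strata in advance (for example 7-8 and 9-10) and state explicitly that no continuity correction is used.
- Report the Mantel-Haenszel odds ratio with its matching interval in place of the unadjusted Wald interval.
- Report Fisher's test as a pre-specified sensitivity analysis. Do not make it a fallback triggered by the observed counts, which would let the data choose the test and could mix tests across weeks and concentrations.
- Update the entry in SAP 15 accordingly. If Fisher's test is kept as the main test, give the reason there and report an interval consistent with it.

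The cost is SAP wording and a few lines of code on data already collected. The downside is an asymptotic test in place of an exact one; in simulation its level stayed at or below about 5% for null rates of 3% to 20%.

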## **13.3 Exploratory Endpoints**

The following categorical exploratory endpoints will be summarized using mITT analysis set. P-values and 95% confidence intervals (CI) will be presented based on Fisher's exact test. In addition, odds ratio (OR) and 95% Wald confidence intervals will also be presented when applicable:

- At least a 50% reduction from baseline in EASI-50 at Week 2 and 4.
- At least a 75% reduction from baseline in EASI-75 at Week 2 and 4.
- At least a 2-grade reduction from Baseline to clear (0) or almost clear (1) in vIGA at

**Week 2 and 4.**

The following continuous exploratory efficacy endpoints will be analyzed using an MMRM model similar to the continuous secondary efficacy endpoints:

- Change from baseline in vIGA at Weeks 2 and 4.

The following exploratory endpoint will be summarized and listed using mITT analysis set and PP set:

- Hourly Pruritus Numeric Rating Scale (NRS) on Day 1.

## 14 SAFETY ANALYSIS

The safety analysis will include reported local and systemic TEAEs and other safety information (i.e., clinical laboratory evaluations, vital signs, physical examinations, ECGs and local tolerability assessments results).

### 14.1 Adverse Events

Adverse events will be coded according to the latest version of the Medical Dictionary for Regulatory Activities (Version 26.1 or later).

Analyses of adverse events will include all events reported from the time of informed consent to 28 days after the last dose of study drug.

See [Appendix 1](#) for handling of completely or partially missing dates for AEs. In the case where it is not possible to define an AE as treatment emergent or not, the AE will be classified as treatment emergent.

A TEAE is any condition that was not present prior to treatment with the trial product but appeared following first dose, was present at treatment initiation but worsened during treatment, or was present at treatment initiation but resolved and then reappeared while the individual was on treatment (regardless of the intensity of the AE when the treatment was initiated) up to and including 28 days post the last dose of the study treatment.

An overall summary table of AEs will be provided. The number of events and the number and percentage of participants who experienced AE, TEAE, TEAE by highest relationship, TEAE by relationship, TEAE by maximum severity, TEAE by severity, related TEAE by maximum severity, related TEAE by severity, serious AE, serious TEAE, serious TEAE by highest relationship, TEAE and related TEAE leading to study treatment discontinuation, TEAE and related TEAE leading to treatment interruption, and AE leading to death will be presented.

Unless otherwise specified, a participant experiencing the same TEAE multiple times will be counted only once for the corresponding PT. Similarly, if a participant experience multiple TEAEs within the same SOC, the participant will be counted only once for that SOC. The summary table of TEAEs will be sorted alphabetically by SOC and within each SOC the PT will be presented by decreasing order of the overall occurrence.

The TEAE will be summarized:

- by SOC and PT within SOC;
- by SOC, PT, and relationship. If a participant experiences more than 1 TEAE within different relationship categories within the same SOC/PT, only the worst case (highest relationship) will be summarized. A TEAE with an unknown relationship will be considered treatment related.
- by SOC, PT, and severity (mild/moderate/severe). If a participant experiences more than 1 TEAE within different severity categories within the same SOC/PT, only the worst case (maximum severity) will be reported. A TEAE with an unknown severity will be considered as severe. A listing of AEs with changing severity will be provided.
- by SOC, PT, relationship, and severity (mild/moderate/severe). Each participant will be counted only once within a SOC or a PT by using (1) the highest relationship followed by (2) the maximum severity. A TEAE with an unknown severity will be considered as severe.

The serious TEAE will be summarized:

- by SOC and PT;
- by SOC, PT, and relationship. If a participant experiences more than 1 serious TEAE within different relationship categories within the same SOC/PT, only the worst case (highest relationship) will be reported.

Listings of all AEs, all AEs leading to death, all SAEs, all TEAEs leading to study drug discontinuation, all TEAEs leading to study drug interruption, and most frequent TEAEs will be provided.

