8.2.5. Recording Adverse Events

Adverse events spontaneously reported by the participant and/or in response to an open question from the trial personnel or revealed by observation will be recorded during the trial at the investigational site. Adverse events that lead to discontinuation of administration of trial drug or withdrawal from study must be reported and recorded as an AE. Information about AEs will be collected from signing of consent form until the end of the trial. Serious adverse event information will be collected from signing of consent form until Week 8 (Day 56), 4 weeks following the last dose of trial drug. The AE term should be reported in standard medical terminology when possible. For each AE, the Investigator will evaluate and report the onset (date and time), resolution (date and time), intensity, causality, action taken, serious outcome (if applicable), and whether or not it caused the participant to discontinue the trial.

Intensity will be assessed according to the following scale:

- Mild (awareness of sign or symptom, but easily tolerated)
- Moderate (discomfort sufficient to cause interference with normal activities)
- Severe (incapacitating, with inability to perform normal activities)

It is important to distinguish between serious and severe AEs. Severity is a measure of intensity whereas seriousness is defined by the criteria under Section 8.2.3. An AE of severe intensity may not be considered serious.

Should a pregnancy occur, it must be reported and recorded on TrialSpark's pregnancy form. Pregnancy in itself is not regarded as an AE unless there is a suspicion that an IP may have interfered with the effectiveness of a contraceptive medication.

The outcome of all pregnancies (spontaneous miscarriage, elective termination, normal birth or congenital abnormality) must be followed up and documented even if the participant was discontinued from the trial.

All reports of congenital abnormalities/birth defects are SAEs. Spontaneous miscarriages should also be reported and handled as SAEs. Elective abortions without complications should not be handled as AEs.

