## 2 STUDY OBJECTIVES AND ENDPOINTS

**Table 1 Objectives and Endpoints**

Objectives	Endpoints
Primary Efficacy:	
To evaluate the anti-pruritic effect of ASN008 topical gel compared to matching vehicle in participants with AD following BID topical application for 4 weeks (28 days).	

Percent change of 7-day average daily peak pruritus NRS from Baseline to Week 4.

Secondary Efficacy	
To evaluate the therapeutic effect of ASN008 topical gel on AD.	

Percent change of 7-day average daily peak pruritus NRS from Baseline to Week 1, 2, and 3.

Change of 7-day average daily peak pruritus NRS from Baseline to Week 1, 2, 3 and 4.

Change and percent change from baseline in daily peak pruritus NRS to Days 1 to 7(Week 1).

Pruritus response defined as 7-day average of daily peak pruritus NRS reduction <math>\geq</math> 4 points from Baseline at Week 1, 2, 3, and 4.

Change from baseline in 5-D Pruritus Scale at Week 2 and 4.

Change and percent change from baseline in the EASI score at Week 2 and 4.

Change from baseline in total BSA at Week 2 and 4.

Change from baseline in the Dermatology Life Quality Index (DLQI) at Week 2 and 4.

Change from baseline in The Patient Oriented Eczema Measure (POEM) at Week 2 and 4.

Objectives	Endpoints
Pharmacokinetics	
To evaluate the pharmacokinetic (PK) profile of ASN008 topical gel in participants with AD following BID topical application.	
 
ASN008 PK will be characterized using population-based methods. Apparent systemic clearance (CL/F), apparent volume of distribution (Vd/F), inter- and intra-participant variability of these parameters will be estimated.
 

Safety	
To evaluate the local and systemic safety and tolerability of ASN008 topical gel in participants with AD following BID topical application.	
 
Number of TEAEs.
 
Number of IP-related TEAEs.
 
Changes in vital signs, physical examinations, ECG, and safety laboratory tests.
 
Incidence of treatment-emergent serious adverse events (TESAEs) from first dose through completion of the follow-up period (up to a maximum of 56 days).
 
Incidence of TEAEs leading to treatment discontinuation from first dose through completion of follow-up period (up to a maximum 56 days).
 

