### 3 STUDY DESIGN

#### 3.1 Overall Design

Approximately 120 participants, at least 18 years of age, with mild to moderate AD (validated Investigator Global Assessment [vIGA] of 2 or 3), BSA of  $\leq 20\%$  involved, and a pruritus NRS  $\geq 7$  at Screening and at Day 1 (pre-dose), will be included in this randomized, double-blind, placebo-controlled, multicenter, Phase 2 trial.

All participants will sign an informed consent form and undergo screening (within 28 days prior to Day 1). With approval from the medical monitor, the screening period may be extended to 7 days in certain situations (i.e., IP (investigational product) shipping delays, laboratory or ECG re-tests, or other logistical or unforeseen issues) that would cause the Day 1 visit to need to occur more than 28 days after the screening visit). During the screening period, all treatments for AD and/or itch will be stopped to allow for wash out, as applicable and according to eligibility requirements. Participants may be re-screened once if they fail the initial screening evaluation for reasons related to incidental transitory conditions and if they met (and continue to meet) the disease severity and pruritus level specified in the inclusion criteria.

Eligible participants will be randomized in a 1:1:1:1 ratio to receive ASN008 gel 1.25%, ASN008 gel 2.5%, ASN008 gel 5.0%, or matching vehicle BID for 4 weeks (28 days), followed by a 4-week (28-day) follow-up period. The first dose of study treatment will be applied on Day 1 and the last dose will be applied during the Day 28 study visit. Participants are not to receive study treatment for more than 28 days. Refer to the Study Schema ([Figure 1](#)) and Schedule of Events ([Table 1](#)) for more details.

Participants will be required to participate in 8 scheduled visits: Screening; Randomization (remote visit); Day 1; Week 1 (Day 8); Week 2 (Day 15); Week 3 (Day 22); Week 4 (Day 28); and Week 8 (Day 56)/early termination (ET).

The trial duration per participant is up to 12 weeks (84 days): including up to 4 weeks (28 days) for the screening period, 4 weeks (28 days) for the treatment period, and up to 4 weeks (28 days) for the follow-up period.

A participant is considered to have reached the end of the trial when they have completed their Day 56 (Week 12) or ET (early termination) visit. The trial will be considered complete when the last participant has completed their last trial visit.

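### The 28-day cut-off for adverse event analyses in SAP 14.1 can fall one or two days short of the window in the plan's own treatment-emergent SAE endpoint

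*SAP*

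**What the plan says.** **Analysis window.** SAP 14.1 has the adverse event analyses cover "all events reported from the time of informed consent to 28 days after the last dose of study drug". It also ends the TEAE definition "up to and including 28 days post the last dose of the study treatment". SAP 15 declares the first limit as a change from the protocol, without giving a reason. It does not list the TEAE limit.

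**Endpoints.** In the objectives and endpoints table (SAP Section 2), treatment-emergent SAEs are counted "from first dose through completion of the follow-up period (up to a maximum of 56 days". TEAEs leading to treatment discontinuation have a near-identical window. Two other safety endpoints, the number of TEAEs and "Number of IP-related TEAEs", carry no window.

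**Collection.** Protocol 8.2.5 says: "Information about AEs will be collected from signing of consent form until the end of the trial". Protocol 8.2.1 also collects to the final visit or contact, and the TEAE definition in protocol 8.2.2 has no upper limit. Yet protocol 8.2.1 and 8.2.3 also speak of recording within 28 days of stopping treatment, and 8.2.5 equates Day 56 with 4 weeks after the last dose.

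**Timing.** SAP 3.1 says "the last dose will be applied during the Day 28 study visit". Protocol Table 2 allows that visit up to 2 days early and the follow-up visit 2 days either side of Day 56. The SAP's schedule of events (Section 3.2) has these two windows the other way round.

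**The concern.** An endpoint and the rule that computes it should cover the same days. Here the endpoint is tied to the end of follow-up and the rule is tied to the last dose. The difference between the two depends on how a participant's visits happened to be scheduled. An event in the last days of follow-up could then count for one participant and not for another, although both events were collected and both lie within the endpoint as written.

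The follow-up visit is also a planned point of detection. Laboratory tests, vital signs, a brief physical examination and local tolerability are all scheduled then, and clinically significant findings become AEs. SAP 14.1 limits the analysis to events *reported* by the cut-off and does not say whether onset date or report date governs. If report date governs, an event that began earlier but was found at a late visit could also leave the summaries.

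**Working it through.** **Inputs**
- Cut-off: last-dose day L plus 28, inclusive (SAP 14.1).
- Endpoint end: completion of follow-up, at most 56 days, read here as Study Day 56 (SAP Section 2; first dose is Study Day 1 by SAP 5.3).
- L: 26, 27 or 28. Protocol Tables 2 and 3 give a window of minus 2 days for the Day 28 visit, as does the SAP's PK sampling table.
- Follow-up day V: 54 to 58 under protocol Table 2; 54 to 56 under the SAP's schedule of events.

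**Step 1: the plan's own figure.** Protocol 8.2.5 treats Day 56 as 4 weeks after the last dose. With L = 28, 28 + 28 = 56, so this reproduces. A visit on Day 56 is then exactly on the cut-off and is included.

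**Step 2: protocol windows.** The visit is past the cut-off when V > L + 28.

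| L | Cut-off | V past the cut-off | Of these, V ≤ 56 | Days from cut-off to Day 56 |
|---|---|---|---|---|
| 26 | 54 | 55, 56, 57, 58 | 55, 56 | 2 |
| 27 | 55 | 56, 57, 58 | 56 | 1 |
| 28 | 56 | 57, 58 | none | 0 |

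- Visit past the cut-off: 4 + 3 + 2 = 9 of 15 combinations. The largest gap is 58 − 54 = 4 days.
- Visit past the cut-off and within the 56-day cap: 2 + 1 + 0 = 3 of 15. The other six have the visit on Day 57 or 58.
- In four of those six (L = 26 or 27), follow-up also covers the one or two days up to Day 56 that the cut-off excludes. Some in-cap days are therefore excluded in 3 + 4 = 7 of 15 combinations, never more than 2 days.

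**Step 3: SAP windows.** With V = 54 to 56 and L = 26 to 28, the count is 2 + 1 + 0 = 3 of 9, and the largest gap is 56 − 54 = 2 days. Taking the SAP's plus or minus 2 days for the Day 28 visit literally (L up to 30) gives 3 of 15, but L = 29 or 30 collides with "Participants are not to receive study treatment for more than 28 days".

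**Step 4: reading of the cap.** If 56 days means elapsed days, the cap is Study Day 57. The in-cap visits past the cut-off become 3 + 2 + 1 = 6 of 15, and the largest in-cap gap is 57 − 54 = 3 days.

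**Step 5: early stopping.** Assume that a participant stops treatment on day L but stays in the study to Day 56. The gap is 56 − 28 − L: 7 days for L = 21, 14 for L = 14 and 21 for L = 7.

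**Step 6: which endpoint.** A TEAE that leads to stopping treatment begins before dosing ends, so a limit 28 days after the last dose removes practically none of these. The endpoint exposed is treatment-emergent SAEs.

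**The case against.** Several points count against making much of this, and most of them stand.

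- **The protocol is mixed.** Sections 8.2.1, 8.2.3 and 8.2.5 contain a limit of 28 days or 4 weeks. The SAP adopted a limit that was already there and declared the AE cut-off in SAP 15. A reader might infer that the SAP departs from a clear protocol rule, but the protocol does not give one clear rule. What remains is the mismatch inside the SAP between 14.1 and its endpoint table.
- **Excluded does not mean lost.** SAP 14.1 lists all AEs and all SAEs. Laboratory, vital-sign, examination and tolerability results have their own summaries in SAP 14.2, 14.3, 14.5 and 14.6, with no 28-day limit. SAP 5.6 says that all safety data enter the non-by-visit tables, which points towards inclusion and itself needs reconciling with 14.1.
- **Findings are not necessarily dated to the visit.** Protocol 8.2.5 records onset date and time. If onset governs, an event found late is excluded only when it began after the cut-off.
- **The counts are not frequencies.** A reader might take 9 of 15 to mean that most follow-up visits fall outside. The documents give no distribution of visit days. If every participant is exactly on schedule (Day 28 and Day 56), none is affected. Days 57 and 58 exceed the endpoint's cap in any case, apart from Day 57 if the cap counts elapsed days.

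None of this removes the core point. A last dose on Day 26 or 27 followed by an on-time Day 56 visit is permitted, inside the endpoint and outside the analysis rule.

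**Conclusion.** The inconsistency is real but small. As written, SAP 14.1 does not deliver the treatment-emergent SAE endpoint for participants whose last dose falls before Day 28. For those who complete treatment, the shortfall within the endpoint is one or two days, reading the cap as Study Day 56. Against the protocol's latest follow-up day it is up to 4 days, part of which lies beyond the endpoint's own limit. It is longer only for participants who stop treatment early and remain in the study, which is an assumption here.

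The documents do not support the stronger readings: that the follow-up visit often falls outside the analysis, that safety events are dropped from the report, or that both windowed endpoints are materially affected. Nothing suggests that the safety conclusions would change. The missing statement on onset or report date deserves correction in its own right, because under a report-date reading earlier-onset events could also be left out. Severity: minor.

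**What to change.** - In SAP 14.1, run the AE analysis window and the TEAE window to the later of 28 days after the last dose and the follow-up/ET visit, and state that onset date governs.
- Align the 56-day cap in the SAP's endpoint table with the permitted follow-up window, and say whether it means study day or elapsed days. The window itself must first be reconciled, because the SAP's schedule of events and protocol Table 2 reverse the Day 28 and Day 56 windows.
- Make SAP 14.1 consistent with SAP 5.6, and reconcile the collection periods in protocol 8.2.1, 8.2.3 and 8.2.5.
- List the change to the TEAE definition in SAP 15, with a reason.

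The cost is SAP wording and one derivation rule. The downside is that a few late, probably unrelated, events would enter the tables.
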